1. STUDY DETAILS

1.1 Study Objectives

1.1.1 Primary Objective

The primary objective of the study is to describe the identification of treatment-emergent pneumonitis by grade (regardless of radiation therapy and/or immune-related etiology) in patients with unresectable Stage III non-small cell lung cancer (NSCLC) receiving durvalumab through the use of mobile technology which collects patient reported outcomes (PROs), vital signs (temperature, heart rate, respiratory rate), oxygen saturation (pulse oximetry), pulmonary function tests (spirometry), and physical movement (number of steps per day).

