1.1.2 Secondary Objectives

[figure not shown]
The secondary objectives are:

- To describe durvalumab treatment discontinuation due to pulmonary Adverse Events (AEs), including pneumonitis
- To describe the duration of durvalumab use
- To describe the incidence of pulmonary AEs by grade
- To describe the severity of pulmonary AEs (including pneumonitis) and use of medication to manage AEs
- To describe the time to development of Grade 3 to 5 AEs, including pneumonitis
- To describe health-related quality of life (QoL) during the study and its relationship with AEs

[figure not shown]

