4.2.2 Secondary Endpoints and Analyses

4.2.2.1 Occurrence of pulmonary AEs, including diagnoses of events, by grade

Definition of pulmonary AE:

- Pulmonary AE is defined as pulmonary adverse event recorded in the CRF. For this study, pulmonary AE do not include pneumonitis event. An AE episode start from onset date of an AE record and stop at the date when AE is resolved. List of terms for pulmonary event can be found in section 8.3.
- Pulmonary AE at diagnosis is defined as the earliest onset of pulmonary AE on or after Day 1, or onset of subsequent AE episode after previously resolved pulmonary AE.
- Highest CTCAE grade of pulmonary AE is defined as the pulmonary AE with the highest CTCAE grade from on or after Day 1 per AE episode. Pulmonary AE with the highest grade can occur on the same date or after the earliest pulmonary AE.
- Patient with response “yes” to CRF question “Is this baseline condition suggestive of a respiratory disease?” and the condition is on-going will not be included in this analysis.

Where there are only limited number of pulmonary AE, listing will be provided including relevant dates, CTCAE grade, and duration, etc.

Where there are sufficient number of pulmonary AE, frequency and percentage (95%CI) of patients with pulmonary AE will be summarized by CTCAE grade for pulmonary AE at diagnosis, and highest CTCAE grade of pulmonary AE and by relationship with pneumonitis.

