If there are limited number of patients with AE events, figure will be produced to show the score change through all time windows with 1 line per patient along with the following labels for AE groups: pneumonitis AEs, other pulmonary AEs.

[figure not shown]
Where there are sufficient number of patients with AE events, the score change from baseline for the scores within time windows at specified time points will be summarized by part and by CTCAE grade (only AEs which has causal relation with durvalumab), mean score change, standard deviation, median, minimum, maximum, and along with the number of patients. The time points are:

- Time Point 1: Prior to the time window which initial pulmonary AE occurred.
- Time Point 2: At the same time window which initial pulmonary AE occurred.
- Or other time point(s) if necessary.

[figure not shown]
The 95% CI of mean score change will be calculated by one-sample t distribution / z distribution depending on sample size. This analysis will be repeated for pneumonitis AEs

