6. CHANGES OF ANALYSIS FROM PROTOCOL

The primary analysis will be descriptive summary of occurrence of pneumonitis by grade. The primary analyses of logistic regression models used for identifying pneumonitis were changed and will be applied to exploratory endpoints which are not covered in this SAP.

CCI

Full analysis set specified in the protocol will not be used in the analysis covered in this SAP.

The analysis of change in QoL will only be applied to the pulmonary AE which has causal relation with durvalumab.

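### The QoL–AE summary counts only AEs attributed to durvalumab, which is narrower than its secondary objective, and SAP 4.2.2.9 and Section 6 do not agree on how far the limit reaches

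*SAP*

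**What the plan says.** The secondary objective, identical in Protocol 3.1 and SAP 1.1.2, is "To describe health-related quality of life (QoL) during the study and its relationship with AEs". It sets no condition on cause.

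SAP 4.2.2.9 gives two outputs, depending on how many patients have events.

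- Few events: "If there are limited number of patients with AE events, figure will be produced to show the score change through all time windows", one line per patient, labelled as pneumonitis or other pulmonary AE. No causality limit is stated here.
- Enough events: score change is tabulated by questionnaire part and CTCAE grade, with the parenthesis "only AEs which has causal relation with durvalumab". A 95% CI for the mean change follows, and then: "This analysis will be repeated for pneumonitis AEs".

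The SAP does not say how many events are enough, or whether they are counted before or after the limit is applied.

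SAP Section 6 lists the limit as a change from protocol: "The analysis of change in QoL will only be applied to the pulmonary AE which has causal relation with durvalumab". The visible text gives no reason. SAP 4.2.2.1 states: "For this study, pulmonary AE do not include pneumonitis event".

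**The concern.** A table meant to show how QoL relates to AEs would show how it relates only to AEs that a physician attributed to durvalumab. That judgement is collected as an AE field (Protocol 8.3.1.3), and the documents give no attribution criteria and no adjudication. It is hard to make in this population. Every patient has had chemoradiotherapy, the SAP's bands for time since radiation start below 14 days (SAP 4.2.4.3), and radiation pneumonitis is one of the six pneumonitis terms (SAP 8.2).

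Three things are at stake. The QoL table could not be read against the event tables beside it, because the events differ. An already small sample shrinks by an unpredictable amount before it is split by grade. And two programmers could build different outputs from the same text. Protocol 4.2 says that findings on secondary endpoints feed the decision on a larger trial, so the table has a use.

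**Working it through.** **1. Event sets side by side**

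| Analysis | Place in SAP | Limited to durvalumab-related AEs? |
|---|---|---|
| Occurrence of pneumonitis | 4.2.1 | No |
| Occurrence of other pulmonary AEs | 4.2.2.1 | No |
| Duration of both | 4.2.2.2 | No |
| Time to Grade 3 to 5 events, both | 4.2.2.7 | No |
| QoL change, few-events figure | 4.2.2.9 | Not stated there; Section 6 could be read as yes |
| QoL change, table, pulmonary AEs | 4.2.2.9 | Yes |
| QoL change, table, pneumonitis | 4.2.2.9 | Yes by natural reading, not explicit |

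QoL is the only one of these with a causality filter.

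**2. Reach of the limit**

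Section 6 is wider than 4.2.2.9 in one respect, because it speaks of the QoL change analysis as a whole and so could include the figure. It is narrower in another, because it names pulmonary AEs, which 4.2.2.1 defines without pneumonitis. The limit reaches pneumonitis only through the closing sentence of 4.2.2.9.

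**3. Size**

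The documents give no number or share of events expected to be judged related, so there is no figure of the plan's own to reproduce on this point. The nearest is Protocol Table 4 (exact intervals for 0 to 16 events among 75). All 12 rows reproduce, but they concern occurrence, not QoL.

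Inputs from the documents:

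- 75 patients (Protocol 9.1, SAP 1.3).
- Any-grade pneumonitis or radiation pneumonitis of 33.9% on durvalumab and 24.8% on placebo, and Grade 3 or 4 of 3.4% on durvalumab, in the Phase 3 trial cited in Protocol 2.2.

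Assumptions:

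- The 33.9% rate applies here.
- No patient is removed for an ongoing baseline condition.
- Each affected patient gives one evaluable change score.
- The share judged related is unknown, so it is varied.

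Expected patients with pneumonitis: 75 × 0.339 = 25.4, taken as 25.

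Half-width of the 95% CI for a mean change, in SD units: t(0.975, k − 1) / √k, where k is the number kept.

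| Share judged related (assumed) | Kept of 25 | Half-width |
|---|---|---|
| 100% | 25 | 2.064/√25 = 0.41 SD |
| 90% | 22 | 2.080/√22 = 0.44 SD |
| 75% | 19 | 2.101/√19 = 0.48 SD |
| 50% | 12 | 2.201/√12 = 0.64 SD |
| 27% | 7 | 2.447/√7 = 0.92 SD |
| 10% | 2 | 12.706/√2 = 8.98 SD |

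The 27% row is the between-arm excess as a share of the durvalumab rate: (33.9 − 24.8)/33.9 = 26.8%. It is one illustrative case, not an estimate of what physicians would decide.

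All rows are before the split by CTCAE grade. At 3.4%, Grade 3 or 4 gives 75 × 0.034 = 2.6 patients before any filter. The documents give no overall rate for the other pulmonary terms in SAP 8.3, so those are not computed.

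**The case against.** The limit is declared, not hidden. The study is a pilot not sized on power (SAP 1.3), and its analyses are descriptive with no formal testing (SAP 4.1). No event is lost to the study: AEs are collected whatever their cause (Protocol 8.3.1.4), the other event analyses are unfiltered, and all AEs are listed (SAP 4.2.4.8). A sponsor may reasonably want to see QoL around drug-related toxicity. Part of Section 6 and the exploratory analyses are redacted, so a reason or an unfiltered analysis may exist out of sight. With few related events the figure may replace the table, and the wide intervals above would then never be computed.

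All of this stands as a bound on the consequence: one descriptive secondary summary is affected, and it can be repaired from data already held. It does not remove the mismatch. Declaring a narrower analysis does not make it answer the broader objective that the SAP keeps, and in a descriptive study the choice of events to describe is the main decision.

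A reader might also infer that the limit contradicts an objective that disregards cause. The words "regardless of radiation therapy and/or immune-related etiology" belong to the primary objective, which is about identifying pneumonitis. They show the study's general approach, but the direct mismatch is with the secondary QoL objective, which is merely unqualified.

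**Conclusion.** The point holds as a mismatch of scope and an inconsistency between two SAP sections. The planned QoL summary answers a narrower question than its objective, on an event set used in none of the occurrence, duration or time-to-event analyses, selected by a judgement for which the documents give no criteria.

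The size cannot be fixed from the documents. Anywhere from none to all of the events could be dropped. On the cited rate, the half-width rises from 0.41 SD with no loss to 0.64 SD at half and 0.92 SD at 27% kept.

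A reader might conclude from the two trial-arm rates that most pneumonitis events would be discarded. That would need fewer than half to be judged related, and the documents do not show it. A difference between arms is not individual attribution, and a physician may judge a radiation pneumonitis event to be related to durvalumab as well. Nor is it established that the event set changes with the output chosen. That follows from 4.2.2.9 read alone, whereas Section 6 can be read as filtering both outputs.

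**What to change.** In SAP 4.2.2.9, make the main QoL–AE summary cover all treatment-emergent pneumonitis AEs and all pulmonary AEs, whatever their cause. Show the durvalumab-related subset as an additional row, which keeps everything the sponsor planned.

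Reword 4.2.2.9 and Section 6 together so that the same event set applies to the figure and the table, pneumonitis is named explicitly as covered, and the count that decides between the two outputs refers to that set. If the related subset keeps a special role, Section 6 should say why.

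The cost is one extra set of table rows and an amended Section 6. Causality is already recorded for each AE, so no new data are needed.

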9.3.1 Efficacy Analyses

PRO values and values from the mobile technology will be considered in connection with events of interest, specifically pneumonitis. Contributions to the identification/prediction of pneumonitis from PROs and variables collected by the devices may be assessed using regression models (e.g. logistic regression) depending on the number of events of interest that are observed in the study; the primary endpoint in these estimations will be the occurrence of pneumonitis. Lagged PRO values and values collected from the mobile technology may be incorporated as covariates in these models; more details will be specified in the SAP. The analyses of the primary endpoint will be conducted by overall patients in the full analysis set (FAS).

Continuous secondary and exploratory endpoints (e.g., duration of durvalumab treatment, duration of pulmonary AE, and absolute QoL and its change from baseline) will be summarized by the number of observations, mean, standard deviation, median, minimum, maximum, and 95% CIs. Categorical variables will be summarized by frequency counts, percentages, and 95% CIs for each category. All descriptive statistics of secondary and exploratory endpoints will be conducted by overall patients in the FAS.

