3.3 Study Endpoints

The definition and analysis of endpoints listed below are described in detail in section 4.2.

The endpoint used to address the primary objective is:

[figure not shown]
- Occurrence of pneumonitis (either radiation or immune-mediated, by grade).
 - Grade of pneumonitis at diagnosis and highest grade of pneumonitis

The endpoints used to address the secondary objectives are:

- Occurrence of pulmonary AEs, including diagnoses of events, by grade
- Duration (days) of pulmonary AEs by type and grade
- Permanent discontinuation of durvalumab due to pulmonary AEs, including pneumonitis
- Early discontinuation of durvalumab treatment for any reason
- Duration (days) of durvalumab treatment
- Treatment interruptions, duration (days) of interruptions, and the reason for interruptions that will be captured in a standard data management form with the site physician documenting reasons in patient charts
- Time (days) to development of Grade 3 to 5 AEs, including pneumonitis
- Prescription of medication used to manage pulmonary AEs and duration (days) of treatment
- Change in QoL scores from baseline

The endpoints used to address the exploratory objectives are:

CCI

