4.2.2.9 Change in QoL assessment scores from baseline

Quality of life assessment questionnaires will be conducted at Baseline visit, every 2 weeks for the first 3 months and once monthly thereafter, and at End-of-Study visit. The questionnaires will include European Organization for Research and Treatment of Cancer Quality of Life Core Questionnaire (EORTC QLQ C30) and Lung Cancer Module (EORTC QLQ LC13). EORTC QLQ C30 will be separated into 3 parts, function scales, symptoms scales and global health status (GHS) [1]. EORTC QLQ LC13 will be measured by 3 parts including lung cancer associated symptoms (cough, haemoptysis, dyspnea, and site-specific pain), treatment-related side effects (sore mouth, dysphagia, peripheral neuropathy and alopecia) and pain medication [2].

Therefore, the assessment scores by these two QoL questionnaires will be summarized by 6 parts as following:

- Part 1: Function scales from EORTC QLQ C30; Higher score signifies higher functional ability (i.e. better quality of life); Item 1-7 and Item 20-27
- Part 2: Symptom scales from EORTC QLQ C30; Higher score signifies stronger symptoms (i.e. worse quality of life); Item 8-19 and Item 28
- Part 3: GHS from EORTC QLQ C30; Higher score signifies higher GHS (i.e. better quality of life); Item 29-30
- Part 4: Lung cancer associated symptoms from EORTC QLQ LC13; Higher score signifies stronger symptoms (i.e. worse quality of life); Item 31-35 and Item 40-42
- Part 5: treatment-related side effects from EORTC QLQ LC13; Higher score signifies stronger side effects (i.e. worse quality of life); Item 36-39
- Part 6: Pain medication from EORTC QLQ LC13; Higher score signifies better pain relief from medication; Item 43

Time windows below will be used to summarize scores by planned data collection time points:

Week	Day	Statistical Analysis Window
Baseline	Day 0	Low – <1
Week 2	Day 11	1 - 21

Week 4	Day 28	22 - 35
Week 6	Day 42	36 - 49
Week 8	Day 56	50 - 63
Week 10	Day 70	64 - 77
Week 12	Day 91	78 - 105
Month 4	Day 120	106 - 135
Month 5	Day 150	136 - 165
Month 6	Day 180	166 - 195
Month 7	Day 210	196 - 225
Month 8	Day 240	226 - 255
Month 9	Day 270	256 - 285
Month 10	Day 300	286 - 315
Month 11	Day 330	316 - 345
Month 12	Day 360	346 - 375

- Inclusion within the time window will be based on the actual date and not the intended data collection time point.
- If there are two scores recorded on the same day, the average of the two records will be used.

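### Every summary statistic of QoL change from baseline in the SAP is tied to AE windows, so the all-patient change summary planned in the protocol is not carried out

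*SAP*

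**What the plan says.** The secondary objective in SAP 1.1.2 has two parts: "To describe health-related quality of life (QoL) during the study and its relationship with AEs". The matching endpoint in SAP 3.3 carries no restriction to patients with AEs: "Change in QoL scores from baseline".

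Protocol 9.3.1 sets the statistics ("absolute QoL and its change from baseline) will be summarized by the number of observations, mean, standard deviation, median, minimum, maximum, and 95% CIs") and the population ("All descriptive statistics of secondary and exploratory endpoints will be conducted by overall patients in the FAS").

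SAP 4.2.2.9 first defines analysis windows from baseline to Month 12: "Time windows below will be used to summarize scores by planned data collection time points". It then splits into two branches according to how many patients have AEs:

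- **Limited number.** A "figure will be produced to show the score change through all time windows with 1 line per patient", labelled by AE group. No summary statistics are specified.
- **Sufficient number.** Change is summarised by questionnaire part and CTCAE grade, for durvalumab-related AEs only, at two named time points. The first is "Time Point 1: Prior to the time window which initial pulmonary AE occurred"; the second is the window of that AE. An open-ended provision allows further time points. The analysis is repeated for pneumonitis.

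SAP Section 6 lists the restriction as a change from the protocol: "The analysis of change in QoL will only be applied to the pulmonary AE which has causal relation with durvalumab". It also drops the full analysis set from the analyses that the SAP covers. SAP Table 1 gives a CI method for QoL change but no population and no time point.

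**The concern.** The endpoint and the first part of the objective concern QoL over the course of the study in all patients. A patient without a qualifying AE has no index window and so cannot enter the SAP's change statistics. The report could then describe QoL change around AEs but have no planned table of mean change by visit for the study population, which is what the protocol set out.

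All patients are asked to complete both EORTC questionnaires every 2 weeks for 3 months and monthly after that. Much of that information would stay outside the change summary. Protocol 4.2 also says that the decision on a larger trial will take the secondary endpoint findings into account, so it matters that the QoL endpoint is reported as defined.

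**Working it through.** The plan states no figure to reproduce here. The point rests on setting the texts side by side; a short calculation then gives the scale.

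**Step 1: what must be delivered.** Protocol 9.3.1 requires n, mean, SD, median, range and 95% CI, for observed QoL and for change, in overall patients. SAP 3.3 keeps the endpoint unrestricted.

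**Step 2: does any SAP text deliver the change part for all patients?**

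- *The window sentence in 4.2.2.9* speaks of scores. It names no change statistic and no population. At most it supports a by-window summary of absolute scores.
- *The limited-number branch* shows change through all windows, but as individual lines, not as a summary.
- *The sufficient-number branch* gives change statistics, but only in the window before and the window of the initial qualifying AE.
- *The provision for further time points* is undefined and sits inside the AE-anchored analysis.
- *SAP 4.1 and Table 1* give default statistics and a CI method. They do not say in whom or when, and the specific text of 4.2.2.9 takes precedence.
- *SAP Section 6* says that the change analysis applies only to durvalumab-related pulmonary AEs.

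None of these specifies an all-patient summary of change by planned time point, and the plainest reading of Section 6 excludes one.

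**Step 3: scale (illustration only).** Inputs: planned N = 75 (SAP 1.3), and 33.9% pneumonitis or radiation pneumonitis of any grade in the durvalumab arm of the earlier phase 3 trial (Protocol 2.2).

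- Expected with pneumonitis: 75 × 0.339 = 25.4, about 25 (95% binomial range 18 to 34).
- Expected without: 75 × (1 − 0.339) = 49.6, about 50.

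The rate for durvalumab-related events is not in the documents. Assumed rates of 20% and 10% give 75 × 0.20 = 15 and 75 × 0.10 = 7.5, about 8 patients.

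**Step 4: precision.** The 95% CI half-width for a mean change, in SD units, is t(0.975, n − 1)/√n:

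| Patients in summary | Half-width (SD) | Relative to n = 75 |
|---|---|---|
| 75 | 0.23 | 1.0 |
| 60 | 0.26 | 1.1 |
| 25 | 0.41 | 1.8 |
| 15 | 0.55 | 2.4 |
| 8 | 0.84 | 3.6 |

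The n = 75 row applies only if every patient has a score in the window; n = 60 allows for attrition. The three smaller rows are before the split by CTCAE grade that the SAP plans.

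**The case against.** The other side has several fair points.

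- **Change is not shown only around AEs.** The limited-number figure runs through all planned windows, and its text does not confine the lines to patients with AEs. In a 75-patient pilot that counts only durvalumab-related events, this branch may well be the one used. This stands as a limit on the point. The figure is still a plot of individuals and does not give the statistics that the protocol planned.
- **QoL during the study is not wholly unreported.** The window sentence, with the defaults in SAP 4.1, can be read as summarising observed scores by window for everyone. This stands for absolute scores. It does not supply the change statistic, and the endpoint is change.
- **The Section 6 sentence is loosely worded.** It could merely repeat which AEs qualify. That reading is possible. Even so, 4.2.2.9 contains no all-patient change summary to fall back on.
- **The narrowing is declared.** This is correct: it is a stated departure, not a hidden omission. Section 6 gives no reason for it, however, and SAP 3.3 was left unrestricted.

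A reader might also infer that change around an AE has no reference at all. The documents do not support that. Each change is measured against the patient's own baseline, and the preceding window is a within-patient reference for the AE window. Separating an AE effect from background decline is a comparative aim that neither document states, and the protocol did not promise a comparison group without AEs.

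**Conclusion.** The point holds for summary statistics of change. As written, the SAP does not carry out the all-patient summary of QoL change planned in Protocol 9.3.1. The unrestricted endpoint in SAP 3.3 and the part of the objective on QoL during the study are left without a change summary, and no reason is given. This follows from the text and does not depend on any event rate.

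The size is illustrative. About 50 of 75 patients would have no pneumonitis if the cited 33.9% applied here, and they would enter the change statistics only through another qualifying pulmonary AE. That rate is any-cause and comes from another trial, so it is not the SAP's durvalumab-related set. Counting only related events could leave fewer patients with a qualifying event; other pulmonary AEs could add some.

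It would go too far to conclude that patients without AEs contribute nothing to QoL reporting: they may appear in the by-window score summary and in the individual-line figure. For a descriptive secondary endpoint in a pilot, this should be corrected, but it does not threaten the primary analysis.

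**What to change.** 1. Add to SAP 4.2.2.9 a table of observed score and change from baseline (n, mean, SD, median, minimum, maximum, 95% CI) for each of the six questionnaire parts at each window already defined, in all safety-set patients with baseline and post-baseline scores. It should be produced whatever the number of patients with AEs.
2. Keep the AE-anchored analysis and the individual-line figure as additions that address the relationship with AEs.
3. Amend the Section 6 sentence so that the restriction to durvalumab-related events applies only to the AE-anchored analysis, and give the reason for it.

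A parallel display for patients without a pulmonary AE or pneumonitis would be a useful descriptive aid, but it is optional because the protocol did not promise it.

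The cost is one standard table. The windows cover 6 post-baseline time points to Week 12 and 9 monthly ones after that, so 15 windows × 6 parts = 90 rows of change. No new data, visits or derivations are needed.

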7.4.3 Quality of Life Assessment Questionnaires

Patients in the study will fill out QoL assessments using the European Organization for Research and Treatment of Cancer Quality of Life Core Questionnaire (EORTC QLQ C30) and the Lung Cancer Module (EORTC QLQ LC13) at the baseline visit prior to treatment being administered, at home every 2 weeks for the first 3 months and once monthly thereafter, and at their End-of-Study visit.

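### The QoL score reported at an AE may come from a form completed before the AE began, because SAP 4.2.2.9 matches form and AE by a shared 14- to 30-day window and not by onset date

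*SAP*

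**What the plan says.** The relationship of QoL to AEs is a secondary objective: "To describe health-related quality of life (QoL) during the study and its relationship with AEs" (SAP 1.1.2, and likewise Protocol 3.1). The EORTC QLQ-C30 and LC13 are completed at baseline, "at home every 2 weeks for the first 3 months and once monthly thereafter", and at the End-of-Study visit (Protocol 7.4.3).

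SAP 4.2.2.9 sets analysis windows for these forms and assigns each form by its date: "Inclusion within the time window will be based on the actual date and not the intended data collection time point". The only rule for more than one score covers same-day duplicates: "If there are two scores recorded on the same day, the average of the two records will be used".

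If enough patients have AEs, the change from baseline is summarised by CTCAE grade, for AEs judged causally related to durvalumab, at these points:

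- A comparison score taken from before the AE's window: "Time Point 1: Prior to the time window which initial pulmonary AE occurred"
- A score meant to represent QoL at the AE: "Time Point 2: At the same time window which initial pulmonary AE occurred"
- An open option with no definition attached: "Or other time point(s) if necessary"

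The summary is repeated for pneumonitis. If few patients have AEs, it is replaced by a figure with one line per patient across all windows.

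**The concern.** Time Point 2 is meant to show QoL when the AE is present. The rule asks only that form and AE share a window. It does not ask which came first, and no other section of either document does. For example, a form on Day 150 and a pneumonitis onset on Day 160 both fall in Month 5 (Days 136 to 165). The Day 150 score then stands as the score at the AE, although the AE had not been recorded as begun. Time Point 1 is by definition earlier, so neither fixed time point is guaranteed to follow onset.

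At stake is the description of how pulmonary AEs and pneumonitis affect QoL. Averaging pre-onset scores with post-onset scores can make that change look smaller than it is. Protocol 4.2 says that positive findings on the secondary endpoints are among the factors in deciding on a larger trial, so the estimate may be used.

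**Working it through.** **Inputs.** Window limits and nominal days are from the table in SAP 4.2.2.9. Neither document gives a distribution of AE onset within a window, so I assume it is uniform. Neither document states a proportion for this analysis, so there is no plan figure to reproduce beyond the table itself. Each nominal day lies within half a day of its window's midpoint.

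**Step 1: form on the nominal day.** For a window from day a to day b with the form on day c, the form predates onset on b − c of the b − a + 1 possible onset days.

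| Window | Days | Length | Nominal day | Onset days after the form | Share |
|---|---|---|---|---|---|
| Week 2 | 1–21 | 21 | 11 | 10 | 47.6% |
| Weeks 4, 6, 8, 10 (each) | e.g. 22–35 | 14 | e.g. 28 | 7 | 50% |
| Week 12 | 78–105 | 28 | 91 | 14 | 50% |
| Months 4 to 12 (each) | e.g. 106–135 | 30 | e.g. 120 | 15 | 50% |

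Pooled over Days 1 to 375: (10 + 4×7 + 14 + 9×15)/375 = 187/375 = 49.9%. With onset limited to Days 1–105 the share is 52/105 = 49.5%, and to Days 1–195 it is 97/195 = 49.7%.

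**Step 2: other form timings.**

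- *Strict 2-weekly dates.* The Week 2 form falls on Day 14 and the Week 12 form on Day 84. Week 2 drops to 7/21 = 33% and Week 12 rises to 21/28 = 75%. Pooled, (7 + 28 + 21 + 135)/375 = 191/375 = 50.9%; for Days 1–105, 56/105 = 53.3%.
- *The same dates, each form 0 to 7 days late (simulated).* The share is 33% to 38%, because a later form leaves fewer onset days after it in the window.
- *All form dates counted from a baseline 0 to 14 days before Day 1, which SAP 3.1 allows (simulated, with forms on time or up to 7 days late).* The share is 47% to 70%, depending on the onset period and on whether the first, closest or last form in the window is used. In these settings 2.5% to 11% of onsets had two forms in their window and 3.2% to 14.5% had none. The SAP has no rule for choosing between forms on different days.

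The simulations leave out the End-of-Study form.

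**Step 3: effect on the mean.** Let p be the share of pre-onset forms, D the mean change carried by post-onset forms and E the mean change carried by pre-onset forms. The Time Point 2 mean is (1 − p)D + pE. Take an illustrative D of 10 points.

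- With E = 0: p = 1/3 gives 6.7, p = 0.5 gives 5.0 and p = 0.7 gives 3.0.
- With E = 5, where half of the effect is already present before the recorded onset: p = 0.5 gives 7.5.

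The bias is toward zero whenever E is smaller than D. Its size depends on p and E, and the documents fix neither.

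**The case against.** A reader might infer that half of the Time Point 2 scores predate the AE, that the QoL effect is therefore halved, and that the plan would find pneumonitis to have little effect on QoL. The documents do not support that.

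- One half follows from uniform onset and forms on nominal days. Neither is stated, and other timings move the share in both directions.
- Halving also needs QoL to change on the recorded onset date and not before. The study is built around the contrary possibility. Protocol 4.2 asks whether variables collected before a pneumonitis event are associated with it, and Protocol 9.3.1 allows lagged PRO values as covariates. If symptoms precede the recorded onset, an earlier form is not free of AE effect.
- All analyses are descriptive without formal testing. This summary is conditional on enough AEs, and the fallback figure shows each patient's scores in later windows too.
- Further time points are allowed, and patients who discontinue are asked for an End-of-Study form (Protocol 5.3 and 7.1.2), which may supply a post-onset score.

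These points limit the size of the problem but do not remove it. The additional time points are undefined and would leave Time Point 2 unchanged. The End-of-Study form reaches only some patients, and no rule says whether it or an earlier form in the window is used. The summary may well run: at the 33.9% any-grade pneumonitis or radiation pneumonitis that Protocol 2.2 cites for durvalumab, 0.339 × 75 is about 25 patients, before the restriction to durvalumab-related AEs and the split by grade. A descriptive mean with a 95% CI can still be mislabelled.

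**Conclusion.** The gap is in the text and needs no assumption: Time Point 2 does not require a form dated on or after onset, so it can report a pre-event score as the score at the event. The share affected is material under every timing examined, at roughly one third to 70%, and about half under uniform onset and nominal form days. The direction of bias is toward zero to the extent that pre-onset scores carry no AE effect. A dilution factor of one half is an illustration and should not be quoted as a property of the plan. The harm is a blurred descriptive estimate for a secondary objective in a pilot study, and no error rate is involved. It is worth correcting because the correction is cheap.

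**What to change.** In SAP 4.2.2.9, replace the two window-based time points with date-based ones, keeping the SAP's restriction to the initial AE:

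- Time Point 1: the last form completed before the onset date.
- Time Point 2: the first form completed on or after the onset date, within a pre-stated maximum number of days (for example, one scheduled form interval).
- Report the days from onset to that form and whether the AE was still ongoing.
- State which form is used when several qualify, including the End-of-Study form.
- Count and report patients with no qualifying form as missing.
- Keep the windows for the by-visit display.

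This needs SAP wording and programming only, since form dates and AE onset dates are already collected. It has two costs. Some patients will have no Time Point 2 score, and the loss may be selective if they died or withdrew. Some qualifying forms will come weeks after onset: with forms on Days 150 and 180, an onset on Days 151 to 165 is first followed by a form 15 to 29 days later, when the AE may have resolved. The cap and the reported lag make this visible but do not remove it.
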